### **8.2. Hypotheses –**

#### **8.2.1. Part 1 is exploratory**

##### **8.2.1.1. Primary Endpoint**

8.2.1.1.1. Percentage of subjects reporting suboptimal adherence to ART therapy on the MAAS. Optimal adherence is measured as a score of 90% or better on Rasch score.

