##### **8.2.1.2. Secondary Endpoints**

8.2.1.2.1. To assess the psychometric properties of the Midland ART Adherence Survey. We will employ a Rasch statistical approach. Rasch Analysis (RA) is a unique approach of mathematical modeling based upon a latent trait and accomplishes stochastic (probabilistic) conjoint additivity (conjoint means measurement of persons and items on the same scale and additivity is the equal-interval property of the scale).

8.2.1.2.2. Identify and classify the case mix or heterogeneity of subjects who report suboptimal and optimal adherence. Optimal adherence is measured as a Rasch score of better than

90% on the Midland AD Adherence scale. Suboptimal is any score 90% or below. Rasch scores range from 0% (no adherence) to 100% (perfect adherence).

### 8.2.2. Part 2

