**8.5.2. Analysis of Secondary End-Points**

8.5.2.1. To assess the psychometric properties of the Midland ART Adherence Survey, we will employ six criteria used in the Rasch approach to evaluating rating scale effectiveness. First, a minimum of 10 observations should be in each category. Second, the shapes of the probability curves should be peaked for each category. Third, the average category measures should increase with the rating scale categories. Fourth, the OUTFIT mean square statistics should be less than 1. Fifth, threshold calibrations should increase with rating scale category. Sixth, the category thresholds should be at least 1.4 logits apart and no more than 5 logits apart.

8.5.2.2. Identify and classify the case mix or heterogeneity of subjects who report suboptimal adherence we will use latent class analysis (LCA); which allows us to identify a finite number of latent subgroups and to explore how treatment effect varies across these subgroups. Such person-centered approaches transcend limitations imposed by diagnostic categories and

classify subjects into latent homogenous classes based on similar response patterns. Latent subgroups of subjects are compared with reference to shape (qualitative differences) symptom levels (quantitative differences).

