## APPENDIX 1: Midland ART Adherence Survey (MAAS)

**Midland ART Adherence Survey**

Survey # \_\_\_\_\_

Age:  18-35  36-49  50-65  66-99      Ethnicity: \_\_\_\_\_      Gender: \_\_\_\_\_How long on ART?  <1 year       1-5 years       6-10 years       11-15 years       16 or more years

1. Do you sometimes forget to take your HIV medications?	 Yes  No	Current prescribed HIV regimen:
3. Have you ever not taken your meds because you felt worse when you took it?	 Yes  No	 Biktarvy  Genvoya  Julica  Triumeq  Isentress/Isentress HD  Stribild  Dulera  Tivicay  Syntuza  Atripla  Complera  Odefsey  Reyataz or Evotaz  Prezista or Prezcobix
4. When you travel or leave home, do you sometimes forget to bring along your medications?	 Yes  No	 Descovy  Truvada  Epzicom  Edurant  Intelence  Sustiva  Selzentry
5. Did you take your HIV medicine yesterday?	 Yes  No	
6. When you feel like your health is good, do you sometimes stop taking your medicine?	 Yes  No	
7. Do you ever miss doses of your medications because of side effects from them? If so, what side effects?	 Yes  No	

8. How often do you take your HIV medications?

- ALWAYS –never miss a dose
- ALMOST ALWAYS-miss 1-2 times a month
- USUALLY-miss 3- 5 times a month
- SOMETIMES-miss more than 5 times, but take more than 5 times a month
- RARELY-take 3- 5 times a month
- ALMOST NEVER-take 1-2 times a month
- NEVER-do not take the medication

9. How many days in the last week did you not take your HIV medication? \_\_\_\_\_

10. How many days in the last month did you not take your HIV medication? \_\_\_\_\_

11. What is your biggest issue with being able to take your medication: \_\_\_\_\_

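### The fourth Rasch criterion puts its OUTFIT limit at the value expected under perfect fit and sets no lower limit

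*Protocol*

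**What the plan says.** Protocol 8.2.1.2.1 lists among the Part 1 secondary endpoints: "To assess the psychometric properties of the Midland ART Adherence Survey. We will employ a Rasch statistical approach". Section 8.5.2.1 says how: "we will employ six criteria used in the Rasch approach to evaluating rating scale effectiveness".

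The fourth of the six reads "Fourth, the OUTFIT mean square statistics should be less than 1". It gives an upper limit only and does not name the unit. No other section mentions OUTFIT.

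The neighbouring criteria are more specific. The first and third name the category ("First, a minimum of 10 observations should be in each category"; "Third, the average category measures should increase with the rating scale categories"). The sixth gives both a lower and an upper limit: "Sixth, the category thresholds should be at least 1.4 logits apart and no more than 5 logits apart".

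In Appendix 1 most closed questions are yes/no. Only question 8 ("How often do you take your HIV medications") has a labelled rating scale, with seven categories. Section 8.2.1 states that "Part 1 is exploratory".

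**The concern.** A fit limit should separate data that follow the model from data that do not. A limit at the expected value under fit does this poorly. Ordinary sampling variation carries some fitting values above it, while responses that are too predictable, as with redundant items, always fall below it. A pass or a fail on this criterion would then say little about the survey.

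At stake is how readable one component of a named Part 1 secondary endpoint will be. The protocol fixes this number itself, so it is not a detail left to a statistical analysis plan.

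**Working it through.** The limit has no derivation in the protocol, so there is no figure to reproduce. The check asks what values the statistic takes when the data fit.

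**1. Expected value.** For a response x with model mean E and variance V, z = (x − E)/√V, and OUTFIT is the average of z² over persons. Under the model the expectation of (x − E)² is V, so the expectation of z² is V/V = 1. This needs no assumption about items or sample, but it does need the true parameters.

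**2. Assumptions for the simulation.** The protocol does not name the exact model or the items to be entered. Assumed: six yes/no items (questions 1 and 3 to 7; question 2 is absent from the text at hand), with difficulties from −1.5 to 1.5 logits; question 8 with thresholds 1.4 logits apart; questions 9 and 10 left out. Person values are normal with (mean, SD) = (0, 1.5), (0, 2) and (1, 1.5). N = 100 and 300, 2000 replicates, item parameters held at their true values, and extreme scores dropped when person measures are estimated. All data fit the model by construction.

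**3. Item level, fitting data.**

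| Person values | Mean OUTFIT | Items at or above 1 | All seven items below 1 |
|---|---|---|---|
| Known | 1.00 | 39–45% | about 1–3% of runs |
| ML | about 0.85 | 19–24% | about 12–22% of runs |

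Estimating person measures shrinks the residuals, most of all for question 8, whose mean falls to 0.57–0.59. Its 95% limits are about 0.42–0.76 at N = 100 and 0.48–0.68 at N = 300, so it never reaches 1. All item failures with ML measures come from the yes/no items, whose upper 97.5% limits run from about 1.4 to 2.2 (N = 100) and about 1.2 to 1.5 (N = 300). The limit of 1 then errs both ways: a yes/no item at 1.1 is ordinary and fails, while question 8 at 0.95 is outside its fitting range and passes.

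**4. Category level, question 8, ML measures.** Among categories that meet the first criterion's 10 observations, about 2–16% reach 1 or more if OUTFIT is the raw mean in the category. At most about 9% do so if that mean is divided by its model expectation. Keeping sparse categories raises the raw-mean figure to 27–33%.

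**5. Overfit.** Take a yes/no item of difficulty b answered without error: yes exactly when the person value t exceeds b. Each z² is then exp(−|t − b|), which never exceeds 1, so the item always passes. With person mean m, SD s and d = m − b, and Φ the normal distribution function, the expected OUTFIT is

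exp(s²/2) × [exp(−d) Φ(d/s − s) + exp(d) Φ(−d/s − s)].

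- d = 0, s = 1.5: 2 × 3.080 × 0.0668 = 0.41.
- d = 0, s = 2: 2 × 7.389 × 0.0228 = 0.34.
- m = 1, b = −1.5 (d = 2.5), s = 1.5: 3.080 × (0.0821 × 0.566 + 12.18 × 0.00077) = 0.17.

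Over the assumed items and populations the range is about 0.17–0.41, using known person values. Milder overfit also passes. Yes/no items with 2, 3 and 5 times the model slope (N = 300, known person values) had mean OUTFIT 0.54, 0.44 and 0.38, and every one was below 1.

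**6. The stated minimum size.** Sections 8.8.1 and 8.8.2 give Part 1 the same minimum as Part 2, namely 30; 6.1.4.3 allows more. Ten observations in each of seven categories need 7 × 10 = 70. At 30, the first criterion already fails for question 8 as printed, whatever the fourth shows.

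**The case against.** Four points can be made for the plan.

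**The lead-in and the other five criteria point to categories.** This stands. Category OUTFIT is the natural reading, and the unnamed unit is a missing detail rather than an error. The item-level rates therefore belong to the less natural reading.

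**On the category reading, fitting data seldom fail.** This largely stands. With estimated measures the rate is small to moderate and depends on formula, estimator and sparse categories. A reader might infer from the expected value of 1 that the rule rejects about half of all fitting items or categories. That holds only roughly, and only with known person values, which an analysis never has.

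**A one-sided screen for noise is coherent if overfit is not the target.** This stands in part. Such a screen still needs a limit above what fitting data produce, and 1 is not above it for the yes/no items.

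**Nothing follows from failing.** This stands. A reader might infer that the primary endpoints are at risk, because 8.5.1.1 and 8.6.1.1 use the Rasch score. The protocol does not make that link: no item is dropped, no score is recalculated and no endpoint is conditioned on this criterion.

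**Conclusion.** The limit is wrong as written. It lies at the expected value under fit, and it cannot flag overfit of any degree. The first part follows from the definition of the statistic with true parameters, and the second from the absence of a lower bound; neither depends on the simulation.

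The size of the effect on fitting data does depend on it. It is 39–45% of items with known person values, 19–24% with ML measures, and about 1–16% of adequately filled question 8 categories with ML measures. These rates rest on the assumed items, populations, N and true item parameters. Joint and conditional ML item estimation were not examined, so no single failure rate is claimed.

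The consequence is limited to the interpretability of an exploratory Part 1 secondary endpoint. The change is worth considering because it is cheap.

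**What to change.** In 8.5.2.1, replace the fourth criterion with a two-sided range fixed before analysis, and name the unit in the same sentence. For example: *Fourth, each category [or item] OUTFIT mean square should lie between the 2.5th and 97.5th percentiles obtained from data simulated to fit the Rasch model with the final item set, estimator and sample size.* If categories are meant, also state the formula, since the raw and the expectation-divided versions behave differently.

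Raising the upper bound above 1 would not be enough on its own. At item level a fitting question 8 lies at about 0.42–0.76 with ML measures, so such a bound would miss substantial misfit there. One common band around 1 has the same weakness.

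The cost is one sentence and one short simulation. The limits will depend on the estimated item parameters. Each value has a 5% chance of falling outside by chance, so seven fitting values give 7 × 0.05 = 0.35 flags on average, and an isolated flag should be read accordingly. Data collection and visits do not change.

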## 8.6. Part 2 –

### 8.6.1. Primary Endpoint

- 8.6.1.1. Percentage of subjects reporting suboptimal adherence, analyzed by intention to treat, from baseline to four-months using Rasch scores. The hypothesis testing will be carried out at the 5% (2-sided) significance level unless otherwise specified. P-values will be rounded to three decimal places. P-values less than 0.001 will be reported as <0.001 in tables. P-values greater than 0.999 will be reported as >0.999.
- 8.6.1.2. We hypothesize that a minimum of 85% of subjects taking DRV/COB/FTC/TAF will demonstrate optimal adherence from baseline to four-months as measured by the Midland ART Adherence Survey. Optimal adherence is defined as a Rasch score greater than or equal to 90%. Rasch scores range from 0% (no adherence) to 100% (perfect adherence).

## 8.7. Part 2 - Analysis of Secondary End-Points

### 8.7.1. These are descriptive endpoints so no hypotheses are tested.

- 8.7.1.1. Change at 4 months from baseline in tolerability measured by standardized patient reported outcome questionnaire.
- 8.7.1.2. Percentage of subjects with greater than or equal to 90% by pill count
- 8.7.1.3. Proportion of subjects that have HIV-1 RNA  $\geq$  50 copies/mL at baseline and at month 4
- 8.7.1.4. Proportion of subjects with significant changes at 4 months from baseline in serum creatinine, AST or ALT
- 8.7.1.5. Change at 4 months from baseline in absolute and percentage CD4.
- 8.7.1.6. Change at 4 months from baseline in absolute and percentage weight
- 8.7.1.7. Number of drug discontinuation for any reason

8.7.2. All data will be summarized. For baseline characteristics and safety outputs a total overall column will be included to summarize all subjects. Data will be summarized by visit. In summary tables of continuous variables, the arithmetic mean (AM), median, 95% confidence interval (CI), standard deviation (SD) and standard error (SE) will be presented to one more decimal place than the original data. In summary tables of categorical variables, counts and percentages will be used.

8.7.3. We will identify and classify the case mix or heterogeneity of subjects adherence we will use latent class analysis (LCA); which allows us to identify a finite number of latent subgroups and to explore how treatment effect varies across these subgroups. Using the clinical, psychosocial and demographic variables we will classify subjects into latent homogenous classes based on similar response patterns.

8.7.4. Using the latent classes identified above we will use class membership (latent class) in a as a predictor of a distal standardized outcome adherence range from 0 to 100.

## 8.8. Sample

8.8.1. All subjects who meet pre-determined criteria from Adherence Survey and meet other eligibility requirements will be offered enrollment into Part II of the study. As Part 1 of the study is tied to Part 2, we will employ the same sampling formulation for minimum sample size.

8.8.2. We follow the work of Viechtbauer et al (2015) to calculate sample size. For encountering a reduction in primary-end-points of 10%, with a 95% confidence interval we use the formula  $n = \ln(1 - 0.95) / \ln(1 - 0.10) = 30$  subjects are needed. This will ensure that we will encounter at least one reduction of the primary end-point at a 95% confidence level.

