#### 3.2.1. Primary Objectives

3.2.1.1. To determine potential changes in ART adherence in subjects who report suboptimal adherence due to side effects from integrase containing regimens switching to Symtuza.

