#### 4.2.1. Primary Endpoint:

4.2.1.1. Change in adherence from baseline to 4 months, measured by adherence surveys

#### 4.2.2. Secondary Endpoints:

4.2.2.1. Change at 4 months from baseline in tolerability measured by standardized patient reported outcome questionnaire

4.2.2.2. Proportion of subjects that have HIV-1 RNA  $\geq$  50 copies/mL at baseline and at Week 16

4.2.2.3. Proportion of subjects with significant changes at 4 months from baseline in serum creatinine, AST or ALT

4.2.2.4. Change at 4 months from baseline in absolute and percentage CD4.

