### 6.2.1. Methodology

6.2.1.1. Part 2 of the study is a prospective cohort analysis of change in adherence, tolerability and safety of subjects who reports poor adherence to ART due to intolerance/side effects from integrase inhibitor containing regimens when they are switched to DRV/COB/FTC/TAF and monitored for 4 months.

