### 6.2.3. Eligibility Criteria

#### 6.2.3.1. Inclusion Criteria

6.2.3.1.1. Meets inclusion criteria of part I of study

6.2.3.1.1.1. Currently on an integrase containing regimen AND

6.2.3.1.1.2. Reports non-adherent due to medication intolerance, defined by pre-determined criteria from Adherence Survey: [indicate a side effect to question 11 OR "yes" to questions 3 OR 7] AND [indicate missing more than 2 doses per month on question 8 OR 9 OR 10]

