#### 8.2.2.1. Primary Endpoint

8.2.2.1.1. Percentage of subjects reporting suboptimal adherence, analyzed by intention to treat, from baseline to 16 weeks.

8.2.2.1.1.1. *We hypothesize that a minimum of 85% of subjects taking DRV/COB/FTC/TAF will demonstrate an optimal adherence score from baseline to four-months as measured by the Midland ART Adherence Survey.* Optimal adherence is defined as a Rasch score greater than or equal to 90%. Rasch scores range from 0% (no adherence) to 100% - (perfect adherence).

8.2.2.2. Secondary Endpoints. These are descriptive endpoints so no hypotheses are tested.

8.2.2.2.1. Change at 4 months from baseline in tolerability measured by standardized patient reported outcome questionnaire

8.2.2.2.2. Percentage of subjects with greater than or equal to 90% by pill count

8.2.2.2.3. Proportion of subjects that have HIV-1 RNA  $\geq 50$  copies/mL at baseline and at month 4

8.2.2.2.4. Proportion of subjects with significant changes at 4 months from baseline in serum creatinine, AST or ALT

8.2.2.2.5. Change at 4 months from baseline in absolute and percentage CD4.

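### The n=30 in 8.8.2 comes from a formula for seeing at least one 10% event, so it does not justify the sample for the Part 2 primary test, and which result carries the 0.05 level is unclear

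*Protocol*

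**What the plan says.** **Sample size.** Section 8.8.2 puts 95% and 10% into n = ln(1-0.95)/ln(1-0.10) and states 30 subjects. It describes the 10% as a reduction in the primary endpoint and adds: "This will ensure that we will encounter at least one reduction of the primary end-point at a 95% confidence level". Section 6.2.2.1 sets the same target enrolment of 30.

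**Hypothesis and test.** Section 8.6.1.2 (and, nearly identically, 8.2.2.1.1.1) states: "We hypothesize that a minimum of 85% of subjects taking DRV/COB/FTC/TAF will demonstrate optimal adherence from baseline to four-months". Optimal means a Rasch score of at least 90%. Section 8.6.1.1 adds: "The hypothesis testing will be carried out at the 5% (2-sided) significance level unless otherwise specified". Section 8.4.1.1 gives the 0.05 level to the Part 2 primary endpoint in order to control the Type I error.

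**What is primary.**
- Objective, 3.2.1.1: "To determine potential changes in ART adherence in subjects who report suboptimal adherence due to side effects".
- Endpoint, 4.2.1.1: "Change in adherence from baseline to 4 months, measured by adherence surveys".
- Methodology, 6.2.1.1: "prospective cohort analysis of change in adherence, tolerability and safety of subjects who reports poor adherence to ART".
- Endpoint in the statistical section, 8.2.2.1.1: "Percentage of subjects reporting suboptimal adherence, analyzed by intention to treat, from baseline to 16 weeks". Section 8.6.1.1 repeats this with four months and Rasch scores.

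**The concern.** Part 2 is set up as a test: it has a stated hypothesis, a two-sided 5% level and a rule reserving that level for one endpoint. A reader therefore expects the sample size section to say what 30 subjects can establish about that hypothesis. It answers another question, namely how many subjects are needed for an event of given frequency to turn up at least once. The 10% enters the formula as a per-subject event probability, although the text calls it a reduction.

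Two things are at stake. First, what n=30 can show depends on the role of the 85%, which the protocol does not state. Second, the 85% hypothesis and a change from baseline can lead to different primary conclusions from the same data, and 8.4.1.1 does not settle which of them is tested at 0.05.

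**Working it through.** **1. The plan's own figure.** Inputs from 8.8.2: probability 0.95, event frequency 0.10.

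n = ln(0.05)/ln(0.90) = 28.43, which rounds up to 29. The stated 30 is acceptably close. At n=30 the chance of at least one event is 1 - 0.90^30 = 0.958. The inputs do not include 85%, a null value, the 5% test level, a power or an SD of change.

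**2. 85% read as the null.** Exact binomial, n=30, upper tail at most 0.025 (the upper half of the two-sided 5% in 8.6.1.1).
- P(X=30 | 0.85) = 0.85^30 = 0.0076, doubled 0.015: rejects.
- P(X≥29 | 0.85) = 0.0480, doubled 0.096: does not reject.

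So only 30/30 shows a rate above 85%. In exact 95% limits, 29/30 has a lower limit of 82.8% and 30/30 has 88.4%. Power is then p^30. The true rates below are assumptions, since the protocol gives none.

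| Assumed true rate | Power at n=30 |
|---|---|
| 90% | 4% |
| 95% | 21% |
| 98% | 55% |

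**3. 85% read as the expected rate.** Same exact test. The nulls are assumptions, since the protocol gives none.

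| Assumed null | Smallest rejecting count | Upper tail under null | Power if true rate is 85% |
|---|---|---|---|
| 60% | 24/30 | 0.017 | 85% |
| 65% | 25/30 | 0.023 | 71% |
| 70% | 27/30 | 0.009 | 32% |

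**4. Precision at n=30.** This needs no null.
- Proportion: 26/30 (86.7%, close to the hypothesised rate) has an exact 95% CI of 69% to 96%.
- Paired change: half-width t(0.975; 29)/√30 = 2.045/5.477 = 0.37 SD of the change scores. The protocol gives no SD, so this cannot be turned into Rasch points.

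**5. The primary result, place by place.**

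| Section | Quantity | Comparison with baseline |
|---|---|---|
| 3.2.1.1, 4.2.1.1, 6.2.1.1 | Change in adherence | Yes |
| 8.2.2.1.1, 8.6.1.1 | Percentage suboptimal, from baseline to 16 weeks or four months | Can be read as dichotomised change |
| 8.2.2.1.1.1, 8.6.1.2 | At least 85% with Rasch score of 90% or more | None stated |
| 8.4.1.1 | The Part 2 primary endpoint, at 0.05 | Does not say which of the above |

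The first and third rows can disagree. Suppose 20/30 subjects are optimal at Week 16 after a much lower proportion at baseline. Adherence has improved. Yet with 85% as the null, P(X≤20 | 0.85) = 0.0097, doubled 0.019, so the two-sided test would find the rate significantly below 85%.

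**The case against.** **Sections 4 and 8 may describe the same thing.** A percentage suboptimal from baseline to 16 weeks can be read as change in dichotomised form, on the same survey, subjects and time points as 4.2.1.1. This stands. A reader might infer that the endpoint statements of sections 4 and 8 flatly contradict each other; the text does not support that. The gap lies in the attached 85% hypothesis, which names no comparator.

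**The design implies a baseline contrast.** Part 2 admits only subjects selected for missed doses: "Reports non-adherent due to medication intolerance, defined by pre-determined criteria from Adherence Survey". Reaching 85% optimal from there suggests improvement. This stands in part, and it would be too strong to say that the hypothesis has no bearing on change. But the screening rule is based on individual survey items, not on the Rasch 90% cut-off, so the baseline optimal rate is neither fixed at zero nor stated.

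**The power figures rest on assumed rates.** True. A reader might infer from step 2 that 30 is too few, especially as a stated minimum of 85% reads naturally as a threshold. The protocol does not fix that reading, and under step 3 with a null of 60% the power is 85%. No single corrected n follows from the document.

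**The SAP may supply the test.** It may, and the choice of test is not at issue. The sample size, its justification, the hypothesis and the primary statements are all fixed in the protocol.

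**Small single-site cohort with descriptive secondary endpoints.** This bears on how serious the point is. It does not make 8.8.2 a justification for the primary test.

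**Conclusion.** The point holds and should be fixed; it does not invalidate the study. The arithmetic in 8.8.2 is acceptable, but it secures only a 95.8% chance of seeing at least one event of 10% frequency. It is not a basis for n=30 with respect to the 85% hypothesis or to a change from baseline, and its wording misdescribes an event probability as a reduction and overstates the guarantee.

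The size depends on what 85% means. Power runs from 4% to 55% if it is the null (assumed true rates 90% to 98%), and from 85% down to 32% if it is the expected rate (assumed nulls 60% to 70%). The figures that need no assumed rate are the 28.4 and 95.8%, the 30/30 requirement if 85% is the null, and the interval of 69% to 96% at 26/30.

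On the primary endpoint the conclusion is narrower: the 85% hypothesis states no baseline comparison, so the result that carries the 0.05 level is unclear.

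**What to change.** 1. In 8.8.2, replace the closing sentence with: *n=30 gives a 95.8% chance of observing at least one event of 10% frequency; this is not a power calculation for the primary hypothesis.* Then state the precision: exact 95% CI 69% to 96% at 26/30, and a half-width of 0.37 SD for a paired change.
2. Reconcile 4.2.1.1 with 8.2.2.1 and 8.6.1 so that one named primary endpoint carries the 0.05 level of 8.4.1.1 and the other is descriptive. Which one is the sponsor's choice.
3. If the 85% hypothesis stays primary, state whether 85% is the null or the expected rate, give the null, and give the power of n=30 against it.
4. If change is chosen, identify the baseline MAAS. Table 6.2.4.1.2 and Appendix 5 schedule the survey at screening, but the visit text in 6.2.4.3 does not list it.

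Cost: protocol wording only, with no extra patients or visits. The downside is that the stated justification for n=30 becomes less favourable.
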